6. STUDY PURPOSES AND OBJECTIVES

6.1 Study purpose

The main purpose of this study is to demonstrate the superiority of Polyoxidonium[®], nasal and sublingual spray, 6 mg/ml (NPO Petrovax Pharm LLC, Russia) therapeutic benefits over placebo in regards to therapy efficacy, when used as part of complex therapy in children aged 1 to 12 years with a diagnosis of ARVI after 7 days of treatment.

6.2 Study objectives

1. To demonstrate the superiority of Polyoxidonium[®], nasal and sublingual spray, 6 mg/ml (NPO Petrovax Pharm, LLC, Russia) efficacy profile over placebo when used as part of complex therapy in children aged 1 to 12 years with a diagnosis of ARVI.
2. To evaluate the safety of the study product of Polyoxidonium[®], nasal and sublingual spray, 6 mg/ml (NPO Petrovax Pharm, LLC, Russia) compared with placebo as part of complex therapy in children aged 1 to 12 years with a diagnosis of ARVI.

7. STUDY DESIGN

7.1 Parameters evaluated during the study

This study assesses the efficacy and safety of nasal and sublingual spray Polyoxidonium[®] (active ingredient of Azoximer bromide) compared with placebo, as part of complex therapy for ARVI not requiring hospitalization in children aged 1–12 years.

Primary efficacy criterion:

- Fever duration period² $\delta = -0.52$ days will be considered as a superiority cut-off level. Axillary body temperature level ≤ 36.9 °C confirmed by two consecutive measurements (morning-evening/evening-morning) will be considered as the end of fever.

Secondary efficacy criteria:

- The dynamics of intoxication symptoms by Days 3, 8 of treatment, assessed according to the Symptom Assessment Scale.
- Assessment of the ongoing therapy efficacy by a physician at the end of treatment course (IMOS scale) - complete recovery (0 points), significant improvement (1 point), minor to moderate improvement (2 points), unchanged (3 points), worsening (4 points).
- Assessment of the ongoing therapy efficacy by the patient's parent/adoptive patient (IMOS scale) - excellent, good, satisfactory, not efficient - scores from 0 to 3.
- Number of cases of the antipyretic product (paracetamol) consumption for the entire study period.
- Number of patients' dropout patients due to the need to prescribe the antibacterial products.
- Number of patients (%) with body temperature normalization (presence of axillary body temperature ≤ 36.9 °C in two consecutive measurements (morning-evening/evening-morning) on Day 5 of therapy.
- Number of patients (%) with clinical pattern normalization on Day 5 of therapy according to the Symptom Assessment Scale (total ≤ 3 points)

Safety endpoints

Safety and tolerability assessments will be conducted throughout the entire study (from the moment of the first use of the study product/ placebo) on the following parameters:

² Axillary body temperature > 37.0 °C confirmed by two measurements (morning-evening/evening-morning)

- frequency of AEs occurrence recorded according to the data of spontaneous patients' reports, presence of complaints, and also to physical examination data, clinically significant deviations of laboratory and instrumental methods of examination from baseline values;

Conclusion on safety of the study product will be made after a statistical assessment of all AEs, including serious ones, which identified at least possible relation to the study product.

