8.1 Inclusion criteria

A patient shall meet the following inclusion criteria:

1. Patients of both sexes aged 1 to 12 years inclusive.
2. Diagnosis of ARVI [ICD-10 code: J00 - Acute nasopharyngitis (runny nose), J02 - Acute pharyngitis, J02.9 - Unspecified acute pharyngitis, Acute laryngitis and tracheitis - J04, J04.0 - Acute laryngitis, J04.1 - Acute tracheitis, J04.2 - Acute laryngitis, Acute upper respiratory tract infections of multiple and unspecified localization - J06, J06.0 - Acute laryngopharyngitis, J06.9 - Acute upper respiratory tract infection, unspecified] confirmed by physician's examination: axillary temperature ≥ 37.0 °C (measured at the moment of physical examination) and Symptom Assessment Scale total score ≥ 5 points, not less than 3 of which should be related to ENT-organs and upper respiratory tract affection (accord. the Symptom Assessment Scale [Appendix 1]).
3. Not more than 24 hours from the onset of ARVI manifestations.
4. Signing an Informed Consent Form by one of the parents/adoptive parent of the child and the child him/herself (if aged ≥ 10 years);

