12.1 Justification of sample size

The study will include patients with a clinically confirmed diagnosis of ARVI (ICD-10 code: J00, J02, J04, J06), who will be randomized and distributed to one of two groups in a 1:1 ratio: Group 1 - patients who will be prescribed the study product as part of complex therapy; Group 2 - patients who will be prescribed a placebo as part of complex therapy.

A similar study of the efficacy, tolerability and safety of Polyoxidonium® in children with acute respiratory infections [5] involved 98 patients (52 in the group of the study product and symptomatic therapy, 46 in the placebo group and symptomatic therapy). The duration of fever and intoxication in the group of the study product was 2.6 ± 0.2 days, in the placebo group - 3.2 ± 0.2 days. Thus, the superiority of the efficacy of the drug Polyoxidonium® over the efficacy of a placebo in relation to the duration of the period of fever and intoxication was $-0,60 [-0,68; -0.52]$ days; the upper limit of the 95% confidence interval for the difference in efficacy of the study product and placebo was -0.52 days. Data from another study, in general, confirms the indicated efficacy values: in children who received Polyoxidonium® in the complex of therapy, compared with children who received only macrolide drugs, their body temperature decreased by 1-2 days earlier, shortness of breath, coughing, wheezing in the lungs (Kuzmenko L.G. The use of Polyoxidonium® in the treatment of frequently ill children, "EFFECTIVE PHARMACOTHERAPY. Pediatrics, No. 2, 2013).

In this study, the fever duration and intoxication period were selected as the main parameter characterizing the efficacy of the therapy. Value of $\delta = -0.52$ days is considered as the margin of excellence.

Calculation of the sample size is based on the following formula:

$$n = (Z_{\alpha} + Z_{\beta})^2 \cdot \frac{2 \cdot SD^2}{(\mu_o - \mu_p - \delta)^2}$$

where, Z_{α} and Z_{β} are critical values of the normal distribution corresponding to the established error levels α and β (α - and β -errors are 0.05 and 0.2, respectively), SD - a standard deviation [25 - 28].

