Appendix 1. Symptom Assessment Scale

Patient's screening No.: □□□

Randomization patient's ID: □□□

To be completed by a physician/patient (on Day 5 of treatment)

Completed on (dd.mm.yyyy): _____ Time of filling out:
_____ h _____ min

Common symptoms of intoxication	Assessment			
Modified/reduced activity (or impaired behavior)	No (0 points)	Mild (1 point)	Moderate (2 points)	Severe (3 points)
Impaired appetite or refusal of feeding	No (0 points)	Mild (1 point)	Moderate (2 points)	Severe (3 points)
Sickly (or different from usual) look	No (0 points)	Mild (1 point)	Moderate (2 points)	Severe (3 points)
Disturbed or altered sleep	No (0 points)	Mild (1 point)	Moderate (2 points)	Severe (3 points)
Nasal Symptoms				
Nasal discharge	No (0 points)	Mild (1 point)	Moderate (2 points)	Severe (3 points)
Nasal congestion/impaired nasal airflow	No (0 points)	Mild (1 point)	Moderate (2 points)	Severe (3 points)
Sneezing	No (0 points)	Mild (1 point)	Moderate (2 points)	Severe (3 points)
Throat and chest symptoms				
Hoarseness	No (0 points)	Mild (1 point)	Moderate (2 points)	Severe (3 points)
Sore throat	No (0 points)	Mild (1 point)	Moderate (2 points)	Severe (3 points)
Cough	No (0 points)	Mild (1 point)	Moderate (2 points)	Severe (3 points)
Total points				

Investigator's Signature: _____

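### The intoxication subscore at Days 3 and 8 is compared without adjusting for its pre-dose value, and little separation between arms can be expected at Day 8

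*Combined protocol and SAP*

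**What the plan says.** Section 7.1 lists as the first secondary efficacy criterion "The dynamics of intoxication symptoms by Days 3, 8 of treatment, assessed according to the Symptom Assessment Scale"; section 10 repeats it, and the synopsis adds that it is measured in points. No section says whether dynamics means the score at the visit or the change from baseline.

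Appendix 1 groups four items under "Common symptoms of intoxication", each scored 0 to 3, so the subscore runs from 0 to 12. The six nasal, throat and chest items run from 0 to 18. Entry (8.1) requires "Symptom Assessment Scale total score ≥ 5 points, not less than 3 of which should be related to ENT-organs and upper respiratory tract affection" and sets neither a minimum nor a maximum for the intoxication items.

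The physician completes the scale at Visits 0, 1, 2 and 3 (9.2, Appendix 5), so a pre-dose subscore should exist for every randomised child. Section 12.2 takes the latest value before the first dose as baseline.

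For quantitative efficacy variables, 12.2 gives a t-test or a Mann-Whitney test between arms, and a paired t-test or Wilcoxon test for paired data. It lists no baseline-adjusted method.

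Section 12.1 gives the expected course from a cited study: "The duration of fever and intoxication in the group of the study product was 2.6 ± 0.2 days", and "in the placebo group - 3.2 ± 0.2 days".

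**The concern.** Two features of the criterion work together. The starting value can differ widely between children: one with 5 nasal or throat points and no intoxication points is eligible, and so is one with 12 intoxication points. A child who starts at 0 cannot show a fall. In addition, Visit 3 falls on Day 8 ± 1, well beyond the durations the plan expects, so most children in both arms may by then score 0.

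If both hold and dynamics is read as change from baseline, the Day 8 comparison is largely a comparison of baseline scores, which randomisation has made equal in expectation. The test would then say almost nothing about the product. At Day 3, where a difference could show, an unadjusted test discards a covariate that has already been collected. At stake is the information in one secondary criterion, not the main conclusion of the trial.

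**Working it through.** **Step 1. Confirm how the plan uses the duration figures.** Inputs from 12.1: means 2.6 and 3.2 days, SD 0.2, margin −0.52, Z values 1.645 and 0.842, cited arm sizes 52 and 46.

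- n = (1.645 + 0.842)² × 2 × 0.2² / (2.6 − 3.2 + 0.52)² = 6.185 × 0.08 / 0.0064 = 77.3, so 78 per group, as stated.
- Interval: −0.60 ± 1.96 × 0.2 × √(1/52 + 1/46) = −0.60 ± 0.079 = [−0.68, −0.52], as stated.

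The plan therefore treats ±0.2 as a between-patient SD. If it were a standard error, the SDs would be 0.2 × √52 = 1.44 and 0.2 × √46 = 1.36.

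**Step 2. Range of the baseline subscore.** The nasal, throat and chest items can supply the whole total of 5, so the minimum intoxication score at entry is 0. The maximum is 4 × 3 = 12. The documents give no distribution within that range.

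**Step 3. Share of children still symptomatic (proxy).** Take the share with duration longer than t days: 1 − Φ((t − mean)/SD) for normal durations, exp(−t/mean) for exponential ones. Use t = 2 for Day 3 and t = 7 for Day 8, both counted from the first dose. The documents do not say whether the durations run from onset or from first dose. Entry is within 24 hours of onset, so counting from onset would move t to roughly 2 to 3 and 7 to 8.

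Power for the difference in shares, with 78 per arm and two-sided 5%, is Φ(|p₁ − p₂| / √{[p₁(1 − p₁) + p₂(1 − p₂)]/78} − 1.96).

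Example, SD 2 and t = 7: p₁ = 1 − Φ(2.2) = 0.0139; p₂ = 1 − Φ(1.9) = 0.0287; SE = 0.0231; power = Φ(0.0148/0.0231 − 1.96) = Φ(−1.32) = 0.09.

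Product against placebo, with power in brackets:

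| Durations | t = 7 | t = 2 | t = 3 |
|---|---|---|---|
| Normal, SD 0.2 (as planned) | 0% v 0% (nothing to detect) | 99.9% v 100% (5%) | 2% v 84% (about 100%) |
| Normal, SD 1 | 0% v 0% (3%) | 73% v 88% (73%) | 34% v 58% (86%) |
| Normal, SD 1.44 and 1.36 | 0.1% v 0.3% (4%) | 66% v 81% (58%) | 39% v 56% (57%) |
| Normal, SD 1.5 | 0.2% v 0.6% (6%) | 66% v 79% (46%) | 39% v 55% (52%) |
| Normal, SD 2 | 1.4% v 2.9% (9%) | 62% v 73% (30%) | 42% v 54% (32%) |
| Exponential (extreme) | 6.8% v 11.2% (16%) | 46% v 54% (14%) | 32% v 39% (17%) |

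At t = 7, out of 78 children per arm, about 1 against 2 remain symptomatic at normal SD 2, and about 5 against 9 under the exponential model. At the early edge of the visit window (t = 6) the power is still only 15% at normal SD 2 and 17% under the exponential model.

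**Step 4. What the Day 8 change then measures.** Write B for the baseline subscore and Y for the Day 8 subscore. If Y ≈ 0, then Y − B ≈ −B, and the difference between arms in mean change is about minus the difference in mean baseline. Randomisation makes that zero on average.

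**Step 5. What adjustment buys.** Suppose baseline and follow-up have equal variance and correlation ρ. The variance of the between-arm difference is then proportional to 1 for the visit score, 2(1 − ρ) for the change and 1 − ρ² for ANCOVA. Since 2(1 − ρ) − (1 − ρ²) = (1 − ρ)² ≥ 0, ANCOVA is in large samples never less precise than either. It also gives the same treatment estimate whether the outcome is the score or the change, which removes the ambiguity over dynamics for that analysis. The documents give no ρ, so the gain cannot be put as a number.

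**The case against.** Several stronger readings are tempting, and the documents do not support them.

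- **The scale cannot register the criterion.** The criterion names Day 3 as well as Day 8, and any child who starts above 0 can show a fall.
- **Many children start at the floor.** Requiring no intoxication points is not the same as having none. Eligible children have a raised temperature, are within a day of onset and may score up to 12; the share at 0 is unknown.
- **Both arms are at zero by Day 8 on the plan's own figures.** The plan gives durations of a combined fever-and-intoxication period, not scores, and nothing maps one to the other. The shares above are a proxy for the planned score tests.
- **Day 3 certainly carries the information.** With the plan's SD of 0.2, power is about 5% at t = 2 and about 100% at t = 3, so the answer depends on a time origin the plan does not state. Under exponential durations Day 3 does no better than Day 8.
- **Baseline imbalance produces false positives.** Chance imbalance is already covered by the 5% error rate. If visit scores are compared, the argument about change does not arise at all.
- **Within-arm tests would be offered as proof of effect.** Section 12.2 lists paired tests generically and 12.4 places within-group comparisons under safety; no efficacy conclusion is tied to them.

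It is also fair to say that Day 8 is the end-of-treatment visit and fits the purpose in 6.1, that it can show late worsening, and that section 12 defers detail to a later analysis plan. These points stand. They limit the concern without removing the case for adjusting for a covariate already in hand.

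**Conclusion.** The point holds in a limited form and is minor. The planned between-arm comparison of the intoxication subscore is unadjusted, although the pre-dose subscore is recorded and entry lets it run from 0 to 12. The Day 8 contrast cannot be expected to separate the arms: power on the proxy is 3 to 9% for normal durations with SD 1 to 2, and about 16% in the exponential case. That conclusion does not depend on the plan's narrow SD. Day 3 may separate them, with power anywhere from about 5% to about 100% according to spread and time origin.

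All of this assumes that the combined fever-and-intoxication durations in 12.1 describe when the subscore reaches 0. The statement that the Day 8 change mirrors baseline further assumes that dynamics means change from baseline. The primary endpoint, the sample size and the type I error rate are not affected.

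**What to change.** In 7.1, 10, 12.2 and the synopsis:

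1. Define the measure as the between-arm difference in the intoxication subscore (0 to 12) at Day 3, and at Day 8 if that time point is kept.
2. Analyse it with adjustment for the pre-dose subscore, by ANCOVA or, if the scores are skewed, by a rank test stratified on baseline. Fix the rule for choosing between them before unblinding. Children with a baseline of 0 stay in the analysis.
3. State that little separation is expected at Day 8, so that a null result there is not read as evidence about the product. Reporting Day 8 descriptively is an option but not a necessity, since it is the end-of-treatment visit; the price would be giving up its p-value.
4. Present within-arm paired tests as descriptive only.

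The cost is wording in the protocol and analysis plan plus one covariate in the model. No new data, visits or patients are needed.

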7.2 Description of the study design

This phase III study (study of the product safety and efficacy in individuals with a specific disease) will be conducted as a multicenter, prospective, randomized, double-blind, placebo-controlled study of the efficacy and safety of study product in children aged 1 to 12 years with a diagnosis of ARVI not requiring hospitalization.

The collection of data from patients during the treatment period of 7 days with a planned visit to monitor the therapy efficacy and safety on Day 8 after the start of treatment with the study product as part of complex therapy, as well as telephone contact on Day 12 ± 1 are sufficient to assess the efficacy and safety profile of study product compared with placebo.

The study will be fully conducted on an outpatient basis. At the same time, Visits 0, 1 and 2 can be carried out by the physician's home visit to the patient.

A total of 4 or 5 patient's visits are expected: Visit 0 (Day -1 - screening), Visit 1 (Day 1 - randomization), Visit 2 (Day 3), Visit 3 (Day 8 ± 1) and Visit 4 (Day 12 ± 1 - telephone contact) (Figure 1). Detailed description of the visits is provided in Section 9.

[figure not shown]

Figure 1. Study flow chart

Signing the informed consent form by one of the child's parents/adoptive parents, and by the child himself/herself (if the child's age is ≥ 10 years old), laboratory tests and assessment of compliance with the requirements of inclusion criteria, non-compliance with non-inclusion criteria will be performed at Visit 0 (Screening). Compliance with the inclusion/non-inclusion criteria requirements will be reassessed at the Visit 1 (Day 1) (may be combined with Visit 0).

At Visit 1 (Day 1) all patients who meet the inclusion criteria and do not meet any non-inclusion criteria will be randomized to two treatment groups in a 1:1 ratio, according to assigned randomization number. One group of patients will receive the study product - Polyoxidonium[®], nasal and sublingual spray, 6 mg/ml (NPO Petrovax Pharm, LLC, Russia), and the other group will receive Placebo, nasal and sublingual spray (NPO Petrovax Pharm, LLC, Russia). The duration of therapy will be 7 days. First administration of SP/placebo (depending on the group) in the sublingual area/nasal passages will be performed at the Visit 1 (Visit 0, if it is combined with Visit 1) in the Clinical Center or at home. During the visit, one of the parents/adoptive parents will be issued and trained how to independently use The study product and antipyretic drugs will be administered at the visit, one of the parents/adoptive parents will be trained for the correct use of dispensed medications at home. Administration of medications to the patient at home will be performed only by one of the parents/adoptive parents.

Visit 2 (day 3) will be conducted at Day 3 of therapy. Clinical signs of bacterial infection overlay should be evaluated by investigator at this visit. By the decision of investigator, the subject will be excluded from the study (if antibacterial therapy is required) or continue study participation and previously prescribed study treatment.

Visit 3 (day 8 ± 1) will be conducted at Day 7 of therapy. Treatment with the study product/placebo will be ended. The visit will include procedures to evaluate efficacy and monitor the safety of treatment.

Visit 4 (day 12 ± 1) is a follow-up visit, it will be performed for safety assessment by the end of the study via a telephone contact. After completion of all Visit 4 procedures the patient will complete study participation.

Throughout the study, the patient is under medical supervision. During this period, the safety and tolerability of the study product/placebo are assessed. Summary schedule of visits and study procedures is given in Appendix 5.

7.3 Minimizing subjectivity

Randomization procedures are used to minimize the possibility of systematic biases and to provide comparability of patients' initial data at the start of treatment and over the whole period of treatment.

7.3.1. Blinding procedure

The whole study will be performed under the conditions of double blinding scenario. The product or placebo in the labeled package (primary and secondary package of products do not differ) is given by the Investigator to the parents/adoptive parents. Product codes are known only to the responsible representative of the Sponsor and the medical representative of the Sponsor.

[figure not shown]
Product codes remain unknown to the Investigator and statisticians until the database lock. Disclosure of the corresponding code is possible only in the case of the registration of any study product related AEs.

7.3.2 Screening and randomization

On Visit 0 (Screening), all patients who previously meet the inclusion criteria and/or the child's parents/adoptive parents receive the detailed information about the study. After signing the Patient Information Sheet with an informed consent form, each patient is assigned a unique four-digit screening number.

Screening No. structure:

• • • • 1 - serial number of the clinical center according to the permission to conduct a study issued by the Ministry of Health of the Russian Federation.

For example: 2 - number reflecting the order of priority of patients' inclusion at each specific clinical center.

In the clinical center No. 2, one out of five patient was enrolled. This study subject shall be assigned a screening number **0205**, where 02 is the center number, 05 is a serial number of the patient enrolled to the study at this clinical center. On Visit 1, all patients who meet all inclusion criteria and do not meet any non-inclusion criteria will be randomized and assigned a three-digit random number.

The distribution of patients into 2 groups in a 1:1 ratio will be conducted according to the randomization scheme of the study protocol.

The randomization scheme will be generated by a separate document and will not be attached to the Study Protocol.

Treatment groups:

Group A: Polyoxidonium[®], nasal and sublingual spray, 6 mg/ml (NPO Petrovax Pharm, LLC, Russia).

Group B: Placebo, nasal and sublingual spray (NPO Petrovax Pharm, LLC, Russia).

Randomization using the electronic system (IWRS).

Each patient will be assigned a randomization number using a special interactive system with Internet access. To gain skills in working with the system, users will be trained and will receive a user manual.

The study will use a competitive set of patients. The number of patients included on the basis of each specific clinical center is not regulated. The recruitment of patients is terminated simultaneously in all centers after randomization of the 172nd patient, whereof the study physicians will be immediately notified.

If a patient early terminates the study, **his/her randomization number will not be reused**, and the discontinued patient cannot be included in the study afterwards. For patients who early terminated the study, the Investigator shall complete the appropriate CRF section.

